1. STUDY OVERVIEW

1.1 GOAL

A retrospective cohort study to discriminate risk for sudden cardiac death (SCD) in patients with Hypertrophic cardiomyopathy (HCM).

1.2 BACKGROUND

Hypertrophic cardiomyopathy (HCM) is a commonly inherited heart muscle disease, which can present in childhood, adolescence or adulthood. It accounts for 42% of childhood cardiomyopathy and has an incidence of 0.47/100,000 children¹. It is a frequent cause of sudden cardiac death (SCD) with those aged between 8-16 years at highest risk^{2,3}.

For adults with HCM, identified risk factors for SCD include non-sustained ventricular tachycardia (VT)^{4,5}, left ventricular (LV) hypertrophy (>3cm)⁶ presence of LV outflow tract obstruction⁷, family history of sudden death², and hypotensive response of blood pressure on exercise testing⁸.

However, the risk factors are less clear in the pediatric population. Historically along with the risk factors listed above, myocardial bridging was thought to be associated with a poor outcome in children with HCM⁹. Other screening tools have included the use of ECG measurements of R and S wave height on ECG along with septal hypertrophy by echocardiogram to predict those at risk for SCD¹⁰. HCM is inherited in an autosomal dominant pattern, the most frequently encountered HCM-associated mutations occur in MYH7 and MYBPC3 genes. To date no correlation has been found between specific genotype and outcome in patients with HCM¹¹. Loar *et al* reported a significant increase in ventricular hypertrophy in genotype positive patients¹². As LV wall thickness remains one of the SCD risk factors in adults, one could postulate therefore that being genotype positive may increase the risk of SCD. Analysis of data from SickKids Hospital (Toronto, ON) in pediatric HCM revealed that mutations in MYH7 gene and a higher number of pathogenic mutations in one or more genes were associated with a higher incidence of major adverse cardiac events¹³. Emerging imaging tools such as Cardiac MRI to determine the presence of Late Gadolinium enhancement may also predict those who have developed myocardial fibrosis and are at risk for SCD^{14,15}.

The European Society of Cardiology (ESC) recently published guidelines on the diagnosis and management of HCM in adults¹⁶ which led to the development of a clinical risk calculator to predict the risk of SCD at 5 years in adults >16 years old¹⁷. This model uses age, maximum LV

wall thickness (mm), left atrial size (mm), maximum LVOT gradient (mmHg), family history of sudden cardiac death, non-sustained VT, unexplained syncope. No such tool exists for children where findings such as being genotyped may have additional risk.

Exercise restriction and β Blocker therapy remains the mainstay of treatment to reduce the risk of SCD in children with HCM¹⁸. Implantation of an implantable cardioverter defibrillator (ICD) is a potentially life-saving therapy for children with HCM, therefore the ability to predict which children are at risk from SCD and who would benefit from an ICD may change the current state of practice. The ESC currently recommends implantation of an ICD after a life-threatening ventricular arrhythmia in children or in those who have two or more major risk factors; however these risk factors have not been clearly defined¹⁶.

1.3 OBJECTIVES

1. To develop and validate a SCD risk calculator that is age-appropriate for children with HCM that includes clinical and genetic factors

2. RESEARCH PLAN

2.1 STUDY DESIGN

This is a retrospective cohort study of pediatric HCM patients using chart and registry review methodology.

2.2 SUBJECT SELECTION

2.2.1 Inclusion Criteria

HCM patients ≤ 18 years of age at first presentation will be included. This includes phenotype positive patients, and phenotype negative gene positive patients considered at risk. Phenotype positive patients are patients with a clinical diagnosis of HCM based on signs, symptoms, family history, EKG and/or echocardiographic features (septal or LV posterior wall thickness z-score (PWd) > +2.0 or ratio of hypertrophied region to PWd > 1.3 in the absence of anatomic LVOT obstruction) of HCM.

2.2.2 Exclusion Criteria

- (i) Neuromuscular, metabolic, syndromic (other than Noonan Syndrome and related RASopathies) or endocrine (including infants of diabetic mothers) causes of HCM
- (ii) Other treatable causes of LVH (systemic hypertension, anatomic defect causing LVOT obstruction e.g. aortic stenosis, subAS, subaortic membrane)

2.2.3 Subject screening

Eligible subjects who were seen since 1990 will be identified through review of the following data sources:

Version: November 30, 2018

- (i) Electronic Medical Records (and paper charts where needed)
- (ii) Other relevant cardiac databases (ie. echocardiography, heart failure)

Patients will be screened for eligibility from participating sites. This is a multi-centre study led by SickKids Hospital (Toronto), participating institutions include Stollery Children's Hospital (Edmonton), BC Children's Hospital (Vancouver), Stanford Children's Health (Palo Alto), Children's Hospital of Philadelphia, Texas Children's Hospital (Houston), Morgan Stanley Children's Hospital (New York), Children's Medical Center of Dallas, University of Michigan Medical Center (Ann Arbor), Cincinnati Children's Hospital, Children's Hospital of Eastern Ontario (Ottawa), The Royal Children's Hospital (Melbourne). REB/IRB approval and service & data transfer agreements will be put in place at each participating centre above as well as new centres that get added.

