3. DATA COLLECTION

3.1 Specific data fields for the initial retrospective review

We will be collecting information on:

- *Screening and demographics*: Variables include eligibility screening and basic demographics such as month/year of birth and gender.
- *Medical history, family history, cardiac work-up*: This information will be captured at the time of first evaluation of HCM (+/-12 months), last reported evaluation and event driven. Events include death, transplant, SCD, aborted SCD, mechanical circulatory support, cardiac surgery, device implantation (e.g. ICD). Data variables to be collected include family history of HCM and sudden cardiac death, history of syncope & history of aborted SCD. Cardiac imaging (echo, cMRI) & other cardiac tests (Holter, exercise) measurements will be captured along with date of test. Management recommendations including exercise restrictions and prescribed medications will also be collected.
- *Genetic testing*: Results of clinical genetic testing will be captured including test used, gene affected and familial inheritance.

Please refer to appendices for detailed case report forms.

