5. STATISTICAL ANALYSIS

5-year SCD risk score will be calculated, and discrimination and accuracy assessments will be performed. Three risk groups (low, medium, high) will be constructed using the calculated risk score. Kaplan-Meier methods with log-rank tests will be used to compare freedom from SCD; competing risk models will be applied to analyze aborted SCD events. C-statistic will be used to quantify the discriminatory ability of the risk scoring, the discrepancy between predicted and observed risk will be also assessed. A revised calculator will be generated from the test cohort using additional variables if needed. This calculator will then be tested in a validation cohort to determine its ability to predict SCD events. We anticipate screening 3,000 HCM patients across all sites of which 70-80% are anticipated to be eligible for inclusion in this analysis. We anticipate that this number will provide enough power based on anticipated SCD event rate of 6% (n=100-150) to develop a new calculator.

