# PRecIsion Medicine in CardiomyopathY (PRIMaCY)

Statistical Analysis Plan

July 21, 2020

All statistical analyses were performed using R version 3.4.1 with survival, multiple imputation by chained equations, mboost, riskRegression, and mlr packages. Clinical characteristics were summarized using descriptive statistics. Continuous variables were summarized using median and interquartile range, whereas categorical variables were summarized using frequencies and proportions. The primary outcome was time to an SCD event during 5-year follow-up defined as a composite outcome of SCD, resuscitated sudden cardiac arrest (including sustained VT/ventricular fibrillation), and aborted SCD events, that is, appropriate shock in a patient with a primary prevention ICD. Event-free survival was estimated by using the Kaplan-Meier method as was the cumulative proportion of SCD events over time.

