#### **Model Development and Performance Assessment**

### General Modeling Approach

To generate a risk prediction model, the relative contribution of the clinical and genetic predictors was quantified by using a competing risk model for SCD events with non-SCD death as the competing risk. This analysis was implemented by using cause-specific regression. To ensure that the quantification was pertinent to the clinical context, patients were administratively censored at 5 years from first evaluation. Two models were considered: a clinical-only model and a clinical/genetic model that included genotype status of the patient. Patients harboring a pathogenic/likely pathogenic causal variant on genetic testing, that is, genotype-positive patients, were compared with patients without a causal variant on testing. We applied a model-boosting algorithm to the cause-specific hazard regression to identify and quantify the association between the candidate risk factors and the composite outcome. For continuous risk factors, the associations were modeled without the assumption of linearity using penalized b-splines. The estimated nonlinear associations were summarized graphically. On the fitting of the 2 boosted models, we then obtained the linear predictors and baseline hazard for the SCD events.

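### Patients qualify by being seen since 1990 but are followed from first evaluation, with no left-truncation method, so any child first evaluated before 1990 biases the absolute 5-year risk downward

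*Protocol*

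**What the plan says.** Three statements set who enters the cohort and when follow-up begins.

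- **Selection.** Protocol 2.2.3 (Subject screening): "Eligible subjects who were seen since 1990 will be identified through review of the following data sources". The only date is attached to being seen.
- **Eligibility.** Protocol 2.2.1 limits age at presentation and sets no calendar limit: "HCM patients ≤ 18 years of age at first presentation will be included".
- **Time zero.** SAP, General Modeling Approach: "patients were administratively censored at 5 years from first evaluation". Protocol 3.1 takes baseline data at the same point: "This information will be captured at the time of first evaluation of HCM (+/-12 months), last reported evaluation and event driven".

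The outcome, in the opening section of the SAP, is time to first event: "The primary outcome was time to an SCD event during 5-year follow-up". It is a composite of SCD, resuscitated arrest and appropriate ICD shock. The estimators are Kaplan-Meier ("Event-free survival was estimated by using the Kaplan-Meier method as was the cumulative proportion of SCD events over time") and a competing-risk model ("This analysis was implemented by using cause-specific regression"). No SAP section mentions delayed entry, left truncation or a restriction on the date of first evaluation.

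**The concern.** The event that brings a patient into the data (a visit in 1990 or later) differs from the event that starts the clock (first evaluation, possibly years before). A child first evaluated in 1984 is in the cohort only if alive and still attending six years later. The whole 5-year window of that child then lies in a period when a fatal event was impossible by construction, yet the analysis counts it as ordinary time at risk. This is left truncation treated as if it were observed follow-up. It lowers the estimated hazard whenever such patients are present and some events are fatal.

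Absolute risk matters here because Protocol section 6 says that the model may inform indications for primary-prevention ICDs. The planned checks may not reveal the error. Calibration in the development data compares predicted with observed risk in the same truncated cohort, so both are low together. A c-statistic responds little to a shift in the baseline hazard. The SAP's Model Validation section gives no entry rule for the replication cohort, so that cohort may carry the same flaw.

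**Working it through.** **1. The plan's own figures.** Protocol section 5 states: "We anticipate screening 3,000 HCM patients across all sites of which 70-80% are anticipated to be eligible for inclusion in this analysis". That gives 3,000 × 0.70 = 2,100 to 3,000 × 0.80 = 2,400 eligible patients. At the anticipated 6% event rate, 2,100 × 0.06 = 126 and 2,400 × 0.06 = 144 events. Both lie inside the stated 100-150.

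**2. Assumptions needed.** The documents do not give the number first evaluated before 1990, the length of follow-up, or the fatal share of events. I assume:
- a true 5-year risk of 6%, treating the protocol's rate as a 5-year risk, with constant hazard λ = -ln(0.94)/5 = 0.01238 per year;
- a 28-year accrual period from 1990;
- exponential follow-up with mean F of 3, 5 or 8 years;
- pre-1990 referral at r = 0.25, 0.5 or 1 times the later rate;
- a fatal share q of SCD events, 0.5 or 1.

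**3. Formulas.**
- Mean time to death or loss before 1990: G = 1/(1/F + qλ).
- Share first evaluated before 1990: f = rG/(rG + 28).
- Immortal years per such patient within the 5-year window: m = G(1 - e^(-5/G)).
- Person-years in the window for a patient first evaluated from 1990 on: a = F(1 - e^(-5/F)).
- Person-years from 1990 on, within the window, for an earlier patient: b = F[(1 - e^(-5/F)) - (5/F)e^(-5/F)].
- Immortal time I = fm; properly observed time A = (1 - f)a + fb.
- Non-fatal events before 1990 do not block selection, so only the fatal share is lost: relative bias = -q × I/(A + I).

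**4. Central case (F = 5, r = 0.5, q = 0.5).** G = 1/(0.2 + 0.0062) = 4.85 and f = 2.425/30.425 = 8.0%. Then m = 3.12, a = 3.16 and b = 1.32. I = 0.0797 × 3.12 = 0.249 and A = 0.9203 × 3.16 + 0.0797 × 1.32 = 3.014. I/(A + I) = 0.249/3.263 = 7.6%, and half of that is 3.8%. The estimated 5-year risk is 1 - exp(-5 × 0.01238 × 0.962) = 5.78%.

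**5. Range.**

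| F (years) | r | q | Share pre-1990 | Hazard understated | 6.0% estimated as |
|---|---|---|---|---|---|
| 3 | 0.25 | 0.5 | 2.6% | 1.2% | 5.93% |
| 5 | 0.5 | 0.5 | 8.0% | 3.8% | 5.78% |
| 8 | 1 | 0.5 | 21.4% | 10.0% | 5.42% |
| 3 | 0.25 | 1 | 2.5% | 2.4% | 5.86% |
| 5 | 0.5 | 1 | 7.8% | 7.3% | 5.57% |
| 8 | 1 | 1 | 20.6% | 19.1% | 4.88% |

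A simulation on the same assumptions agreed to within 0.5 percentage points of relative bias in every row.

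**6. A simpler cross-check.** Fix f directly, assume complete 5-year follow-up, and spread the gap from first evaluation to 1990 uniformly over 0 to D years, with D from 5 to 18. With half the events fatal, 6.0% is estimated as 5.88-5.93% at f = 5%, 5.76-5.86% at f = 10% and 5.52-5.71% at f = 20%. These biases are somewhat smaller, because with complete follow-up the immortal years are a smaller fraction of all person-time. The direction is the same.

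**7. Does the remedy work?** In a simulated extreme (even accrual 1972-2018, 23% of selected patients first evaluated before 1990, all events fatal), the analysis as written gives 4.80% against a true 6.0%. Restriction to first evaluation from 1990 on gives 5.99%, and so does delayed entry at 1990.

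**The case against.** **The phrase may be loose.** It introduces a list of record sources under a screening heading, and the sponsor may have meant first seen since 1990. That reading would remove the problem. But the protocol writes of first presentation and first evaluation where it means them, so the literal reading is any visit. With at least twelve institutions screening, the rule needs one meaning either way.

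**No input to the size comes from the documents.** This stands. If nobody in the analysis was first evaluated before 1990, the bias is nil.

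**The outcome is a composite.** This also stands, and it limits the size. A reader might infer that the modelled risk is understated by about 20%. That applies only to the top of the range with every event fatal. Children resuscitated or shocked before 1990 could still be seen later, so the composite is affected less.

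**Calibration in the replication cohort could expose underprediction.** It could, if that cohort was selected differently. The SAP does not say how it was selected.

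**Predictor effects.** A reader might also infer that survivor selection distorts the coefficients. The documents give nothing from which to work that out and I have not calculated it, so the point is confined to absolute risk.

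**Rerunning is not free.** The SAP is written in the past tense, so a change now means imputing, tuning, fitting and validating again. That is fair, and it is counted in the cost below.

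**Conclusion.** The concern holds for the plan as written. Selection by any visit since 1990, a clock that starts at first evaluation, and no handling of left truncation together bias the absolute 5-year risk downward if any child first evaluated before 1990 is included. With 3% to 21% of the cohort in that position and half of SCD events fatal, the composite hazard is understated by about 1% to 10%, centrally about 4%, or 6.0% read as about 5.8%. If all events are fatal the figures roughly double. These sizes rest on assumed follow-up, referral rates, fatal share and constant hazard. The direction does not depend on those values, provided some events are fatal. The documents do not show that such patients were in fact analysed, so it would go too far to say that every predicted risk is too low. The correction is worth making because the product is an absolute risk and the restriction is simple.

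**What to change.** State in Protocol 2.2.1 or 2.2.3, and in the SAP, that first HCM evaluation must fall on or after 1 January 1990. Report how many patients were first evaluated earlier. If the model is already fitted, refit it without those patients as a sensitivity analysis and compare the baseline hazard and the predicted 5-year risks. State the entry rule of the replication cohort too.

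Delayed entry is an alternative only if the date of the first visit since 1990 is available. Protocol 3.1 lists first, last and event-driven evaluations, not that visit, and the case report forms are not among the documents supplied.

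Cost: a sentence in each document and a filter on the date of first evaluation, provided that date is recorded. If analysis is complete, the imputation, tuning, fitting and validation must be run again. A few early patients are lost.

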3. DATA COLLECTION

3.1 Specific data fields for the initial retrospective review

We will be collecting information on:

- *Screening and demographics*: Variables include eligibility screening and basic demographics such as month/year of birth and gender.
- *Medical history, family history, cardiac work-up*: This information will be captured at the time of first evaluation of HCM (+/-12 months), last reported evaluation and event driven. Events include death, transplant, SCD, aborted SCD, mechanical circulatory support, cardiac surgery, device implantation (e.g. ICD). Data variables to be collected include family history of HCM and sudden cardiac death, history of syncope & history of aborted SCD. Cardiac imaging (echo, cMRI) & other cardiac tests (Holter, exercise) measurements will be captured along with date of test. Management recommendations including exercise restrictions and prescribed medications will also be collected.
- *Genetic testing*: Results of clinical genetic testing will be captured including test used, gene affected and familial inheritance.

Please refer to appendices for detailed case report forms.

4. DATA STORAGE AND CONFIDENTIALITY

All efforts will be made to protect the privacy of individuals in the study. All subjects will be given de-identified study IDs. The link between study ID and the patient identifiers will be maintained locally in a separate, password protected spreadsheet with access limited to study coordinators. De-identified data will be stored using an external REDCap study database that is a web-based program that runs on a dedicated server located within SickKids Hospital. The server, back-up client software, and back-up tapes are supported through SickKids Center for Computational Medicine. The database protects privacy by allowing only site-specific access to research staff from any site to only view the information captured at their sites with the exception of the central repository located at SickKids which will manage all de-identified data.

5. STATISTICAL ANALYSIS

5-year SCD risk score will be calculated, and discrimination and accuracy assessments will be performed. Three risk groups (low, medium, high) will be constructed using the calculated risk score. Kaplan-Meier methods with log-rank tests will be used to compare freedom from SCD; competing risk models will be applied to analyze aborted SCD events. C-statistic will be used to quantify the discriminatory ability of the risk scoring, the discrepancy between predicted and observed risk will be also assessed. A revised calculator will be generated from the test cohort using additional variables if needed. This calculator will then be tested in a validation cohort to determine its ability to predict SCD events. We anticipate screening 3,000 HCM patients across all sites of which 70-80% are anticipated to be eligible for inclusion in this analysis. We anticipate that this number will provide enough power based on anticipated SCD event rate of 6% (n=100-150) to develop a new calculator.

6. CLINICAL RELEVANCE

Children with HCM remain at high risk for SCD. Current clinical risk factors are largely extrapolated from the adult population where a model has been developed to predict those who are at risk of SCD at 5 years^{16,17}. The ability to predict those at risk for SCD in the pediatric population using a prediction model may guide frequency of patient surveillance in those who are at higher risk and may inform indications for ICD insertion for primary prevention. Ultimately this may improve long term outcomes in this population.

7. TIMELINE

We anticipate 12 months for data collection after REB approval and approval of MTAs, 12 months for data analysis and write-up of risk calculator.

# PRecIsion Medicine in CardiomyopathY (PRIMaCY)

Statistical Analysis Plan

July 21, 2020

All statistical analyses were performed using R version 3.4.1 with survival, multiple imputation by chained equations, mboost, riskRegression, and mlr packages. Clinical characteristics were summarized using descriptive statistics. Continuous variables were summarized using median and interquartile range, whereas categorical variables were summarized using frequencies and proportions. The primary outcome was time to an SCD event during 5-year follow-up defined as a composite outcome of SCD, resuscitated sudden cardiac arrest (including sustained VT/ventricular fibrillation), and aborted SCD events, that is, appropriate shock in a patient with a primary prevention ICD. Event-free survival was estimated by using the Kaplan-Meier method as was the cumulative proportion of SCD events over time.

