### Model Tuning

To tune the boosting model, we applied 10 repeated 4-fold cross-validations to determine the hyperparameter of the boosting model. In this exercise, we considered a small learning rate (step size) of 0.01 and a large number of steps. Within each cross-validation iteration, we imputed the missing values by using multiple imputation by chained equations before training the model. The plausibility of missing at random assumed in the imputation depends on the candidate risk factors. As long as the candidate risk factors considered in the study are comprehensive, as in our study, this assumption is reasonable. Next, we applied the trained model and calculated the c-statistic on the cross-validation data for each step. The optimal number of steps (ie, the value of the boosting model hyperparameter) was the one that maximized the c-statistic averaged over all cross-validation iterations. The final model was then fitted using all data with the optimal hyperparameter value estimated in the model-tuning exercise. Given the competing risk data, separate cause-specific hazard regression models were fitted and tuned: 1 for SCD events and the other for non-SCD deaths. Because of a small number of patients with non-SCD deaths, we only applied 3-fold cross-validation to identify and quantify the risk factors associated with non-SCD deaths.

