### Model Performance

On model fitting, both prognostic index and the 5-year cumulative proportion of SCD events were quantified for each patient. The discriminatory power of the final model was quantified using the c-

statistic for competing risk models. Model calibration was assessed by stratifying patients into 3 risk groups based on tertiles of the predicted 5-year probability of a SCD event and by creating a calibration curve to show the relationship between the observed and predicted 5-year probability of events.

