## Model Validation

The final model was externally validated using an independent replication cohort. The Harrell c-statistic was calculated, and calibration curves were constructed using quantiles of predicted risk as described above.

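### Lowest severity: the SAP describes the cumulative proportion of SCD by Kaplan-Meier although it treats non-SCD death as a competing risk, which overstates that one figure slightly

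*SAP*

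**What the plan says.** The opening section of the SAP defines the primary outcome as time to a composite SCD event within five years and then gives the descriptive estimator: "Event-free survival was estimated by using the Kaplan-Meier method as was the cumulative proportion of SCD events over time".

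General Modeling Approach builds the prediction model by "using a competing risk model for SCD events with non-SCD death as the competing risk". Model Tuning adds that "separate cause-specific hazard regression models were fitted and tuned: 1 for SCD events and the other for non-SCD deaths". It gives no count of those deaths, but explains a reduced cross-validation scheme with the words "Because of a small number of patients with non-SCD deaths".

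Model Performance says that, once the model was fitted, "both prognostic index and the 5-year cumulative proportion of SCD events were quantified for each patient". It describes the discrimination measure as a c-"statistic for competing risk models". Under Model Validation, "The final model was externally validated using an independent replication cohort", and there "The Harrell c-statistic was calculated".

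Protocol section 5 plans Kaplan-Meier curves with log-rank tests for freedom from SCD and mentions competing risk models only for aborted SCD. Neither document names a cumulative incidence estimator for the descriptive figure.

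**The concern.** A child who dies of another cause can no longer have an SCD event. A Kaplan-Meier curve for SCD alone has no place for such a death except as a censored observation. It then treats that child as having the same future SCD risk as the children still under follow-up. One minus Kaplan-Meier therefore estimates SCD risk in a hypothetical population without other deaths, and it lies above the proportion who actually have an SCD event. The SAP recognises this in its model, since it fits a separate hazard for non-SCD death, but not in its descriptive estimate.

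At stake is a reported cumulative proportion that is a little too high. A reader may set it beside the model's five-year predictions, which the SAP calls by nearly the same name.

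A smaller point concerns discrimination. The c-statistic is labelled differently in development and in validation, and neither label says how non-SCD deaths enter. A reader cannot confirm that the two figures are like for like.

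**Working it through.** **Inputs from the documents.** Protocol section 5 gives 3,000 screened, 70-80% eligible, an SCD rate of 6% and 100-150 events. The SAP gives the five-year horizon and says that non-SCD deaths were few.

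**The plan's own figure.** 3,000 × 0.70 × 0.06 = 126 and 3,000 × 0.80 × 0.06 = 144 events. Both lie within the stated 100-150. The 6% has no time horizon in the protocol; it is taken here as the five-year incidence.

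**Assumptions.** Five-year non-SCD death p of 1%, 2% or 3%, with 10% as an outer bound that fits poorly with the SAP's description. Hazards are constant.

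**Formulas.** With true five-year SCD incidence F:
- total hazard H = −ln(1 − F − p)/5
- SCD hazard h = H × F/(F + p)
- one minus Kaplan-Meier = 1 − exp(−5h)

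**Worked case, F = 6%, p = 1%.** 5H = −ln(0.93) = 0.07257; 5h = 0.07257 × 6/7 = 0.06220; 1 − exp(−0.06220) = 6.031%.

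| F | p | One minus Kaplan-Meier | Excess (points) |
|---|---|---|---|
| 6% | 1% | 6.031% | 0.031 |
| 6% | 2% | 6.062% | 0.062 |
| 6% | 3% | 6.094% | 0.094 |
| 6% | 10% | 6.329% | 0.329 |
| 100/2,400 = 4.17% | 1-3% | 4.188-4.231% | 0.021-0.065 |
| 150/2,100 = 7.14% | 1-3% | 7.180-7.255% | 0.037-0.112 |

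**Against sampling error.** The standard error of a 6% risk is √(0.06 × 0.94/n), which is 0.52 points at n = 2,100 and 0.48 at n = 2,400. The largest ratio at F = 6% and p = 3% is 0.094/0.485 = 0.19. If the children were split evenly into two cohorts (an assumption), n would be 1,050-1,200, the standard error 0.73-0.69 points, and the ratio smaller. Censoring before five years would widen the standard error further.

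**The c-statistics, in case they are different indices.** Suppose Harrell's c censors non-SCD deaths, while the competing-risk c keeps those children as non-events to five years. Assume F = 6%, a standard normal marker and a log hazard ratio of 0.75 per SD for SCD. Harrell's c minus the competing-risk c, by numerical integration over p = 1-3%, is:

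| Log hazard ratio for non-SCD death | No loss to follow-up | 15% per year loss (assumed) |
|---|---|---|
| 0.75 | +0.0011 to +0.0032 | +0.0016 to +0.0039 |
| 0 | 0.0000 to 0.0001 | about 0.0005 |
| −0.75 | −0.0008 to −0.0023 | −0.0003 to −0.0017 |

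The Hanley-McNeil standard error at an assumed c of 0.70 is 0.0267 with 126 events and 0.0249 with 144. The largest ratio is 0.0039/0.0249 = 0.16. The sign depends on how the marker relates to non-SCD death, which the documents do not say.

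**The case against.** The strongest reply is that nothing of consequence follows. The SAP's product is the risk model, and that model sits in a competing-risk framework. The Kaplan-Meier sentence describes the cohort, the deaths at issue were few, and the excess is well inside sampling error. The death rates used above are assumptions. All of this stands, and it is why the point carries the lowest severity. It does not make the estimator right: the bias is upward whenever non-SCD deaths are censored before five years, the SAP confirms that such deaths occurred, and nothing elsewhere corrects the descriptive figure.

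A reader might infer more than the text supports in three ways.

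- **That the individual predictions are inflated.** Model Performance derives them after fitting the competing-risk model and does not say that Kaplan-Meier was used.
- **That calibration is biased.** The SAP does not name the estimator of observed risk in the calibration curves, so no error can be claimed there.
- **That validation used a different or more favourable c-statistic.** A Harrell-type concordance can keep competing deaths as non-events, so the two labels may describe one index. Even if they do not, the table above shows that the gap could go either way.

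It is also fair to say that context separates the observed curve from the per-patient prediction, despite the shared term. Finally, Kaplan-Meier for event-free survival is sound if every death counts as an event. The SAP does not define that endpoint, and it is not criticised here.

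**Conclusion.** The descriptive estimator of the cumulative proportion of SCD is inconsistent with the SAP's own treatment of non-SCD death, and it is biased slightly upward. At 6% five-year incidence and an assumed 1-3% non-SCD death, the excess is about 0.03-0.09 points (0.5-1.6% in relative terms), at most about one fifth of a standard error. Even at 10% non-SCD death it is 0.33 points. These sizes rest on constant hazards, on reading the protocol's 6% as a five-year figure, and on death rates that the documents do not give. No conclusion of the study would change.

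The c-statistic labels are a matter for clarification, not an established error. Any gap would be a few thousandths, in a direction that the documents do not determine.

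**What to change.** Replace Kaplan-Meier with the Aalen-Johansen estimator for the cumulative proportion of SCD, with non-SCD death as the competing event: sum, over SCD event times, the probability of being free of both events just before that time multiplied by the number of SCD events divided by the number at risk. Event-free survival can stay as it is.

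The cost is a short re-analysis, because the SAP reports the work as already done. The survival and riskRegression packages that it lists are sufficient. The reported figure becomes slightly lower.

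As a secondary clarification, add a sentence saying how each c-statistic handles non-SCD deaths, and report the same index in both cohorts where the data allow. A competing-risk index in the replication cohort requires non-SCD deaths to be identified there, which Model Validation does not confirm. If they cannot be identified, Harrell's c reported in both cohorts, computed the same way, would keep the comparison like for like.
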